## **7.5 Preparation/Handling/Storage/Accountability**

The IP/AxMP must be stored in a secure area according to local regulations. It is the responsibility of the investigator, or designee where permitted, to ensure that IP/AxMP is only dispensed to study participants. The IP/AxMP must be dispensed only from official study sites by authorized personnel according to local regulations.

The product storage manager should ensure that the study intervention is stored in accordance with the environmental conditions (temperature, light, and humidity) as determined by BMS. If concerns regarding the quality or appearance of the study intervention arise, the study intervention should not be dispensed, and BMS should be contacted immediately.

Study intervention not supplied by BMS will be stored in accordance with the package insert.

IP/AxMP documentation (whether supplied by BMS or not) must be maintained that includes all processes required to ensure the drug is accurately administered. This includes documentation of drug storage, administration and, as applicable, storage temperatures, reconstitution, and use of required processes (eg, required diluents, administration sets).

- The investigator or designee must confirm appropriate temperature conditions have been maintained during transit for all study intervention received and any discrepancies are reported and resolved before use of the study intervention.
- The investigator, institution, or the head of the medical institution (where applicable) is responsible for study intervention accountability, reconciliation, and record maintenance (ie, receipt, reconciliation, and final disposition records).
- Further guidance and information for the final disposition of unused study interventions are provided in [Appendix 2](#) and the Pharmacy Manual.

### **7.5.1 *Retained Samples for Bioavailability/Bioequivalence/Biocomparability***

Not Applicable.

## **7.6 Treatment Compliance**

Treatment compliance will be monitored by drug accountability as well as the participant's medical record and electronic case report form (eCRF). This will be source data reviewed through regularly scheduled monitoring visits.

## 7.7 Concomitant Therapy

### **7.7.1 Prohibited and/or Restricted Treatments**

### 7.7.1.1 *Prohibited Treatments*

A horizontal bar chart with 10 bars. The bars are black with white outlines. The lengths of the bars decrease from left to right. The first bar is the longest, followed by a white space, then a shorter black bar, and so on. The last bar is the shortest.

### **7.7.2 Other Restrictions and Precautions**

Participants with a condition requiring long term systemic treatment with either corticosteroids (> 10 mg daily prednisone equivalent) or other immunosuppressive medications. Inhaled or topical steroids, and adrenal replacement steroid doses > 10 mg daily prednisone equivalent, are permitted in the absence of active autoimmune disease.

Participants are prohibited from joining another interventional clinical trial if they are still on study treatment. Participation in observation only studies is allowed at any time.

### 7.7.2.1 SARS-CoV-2 Vaccination Guidelines

### **7.7.2.2 *Imaging Restriction and Precautions***

It is the local imaging facility's responsibility to determine, based on participant attributes (eg, allergy history, diabetic history, and renal status), the appropriate imaging modality and contrast regimen per imaging study. Imaging contraindications and contrast risks are to be considered in this assessment. Participants with renal insufficiency are to be assessed as to whether or not they should receive contrast and if so, which contrast agent and dose is appropriate based on local standard of care.

Specific to MRI, participants with severe renal insufficiency (ie, estimated glomerular filtration rate (eGFR) < 30 mL/min/1.73 m^2) are at increased risk of nephrogenic systemic fibrosis, therefore MRI contrast is contraindicated. Participants may be excluded from MRI if they have tattoos, metallic implants, pacemakers, etc., following local standard of care.

Gentle hydration before and after IV contrast should follow local standard of care. The ultimate decision to perform MRI in an individual participant in this study rests with the site radiologist, the Investigator, and standards set by the local Ethics Committee.

## **7.8 *Continued Access to Study Intervention After the End of the Study***

At the end of the study, BMS will not continue to provide BMS-supplied study intervention to participants/investigators unless BMS chooses to extend the study. The investigator should ensure that the participant receives appropriate standard of care to treat the condition under study.

BMS reserves the right to terminate access to BMS-supplied study intervention if any of the following occur: a) the study is terminated due to safety concerns; b) the development of nivo + rela FDC is terminated for other reasons, including, but not limited to, lack of efficacy and/or not meeting the study objectives; c) the participant can obtain medication from a government-sponsored or other health program. In all cases, BMS will follow local regulations.

## **8 *DISCONTINUATION CRITERIA***

### **8.1 *Discontinuation From Study Treatment***

Participants MUST discontinue IP (and Non-IP/AxMP at the discretion of the investigator) for any of the following reasons:

- Participant's request to stop study intervention. Participants who request to discontinue study intervention will remain in the study and must continue to be followed for protocol-specified follow-up procedures. The only exception to this is when a participant specifically withdraws consent for any further contact with him/her or persons previously authorized by the participant to provide this information

- Any clinical AE, laboratory abnormality, or intercurrent illness which, in the opinion of the investigator, indicates that continued participation in the study is not in the best interest of the participant
- Termination of the study by BMS
- Loss of ability to freely provide consent through imprisonment or involuntarily incarceration for treatment of either a psychiatric or physical (eg, infectious disease) illness. (Note: Under specific circumstances and only in countries where local regulations permit, a participant who has been imprisoned may be permitted to continue as a participant. Strict conditions apply, and BMS approval is required.)
- Disease recurrence [REDACTED]
- [REDACTED]
- Pregnancy (refer to [Section 9.2.5](#))
- Significant noncompliance with protocol (eg, procedures, assessments, medications, etc.). The investigator should discuss such issues with the Medical Monitor/designee and be documented.

Refer to the Schedule of Activities for data to be collected at the time of treatment discontinuation and follow-up and for any further evaluations that can be completed.

All participants who discontinue study intervention should comply with protocol-specified follow-up procedures as outlined in [Section 2](#). The only exception to this requirement is when a participant withdraws consent for all study procedures, including post-treatment study follow-up, or loses the ability to consent freely (eg, is imprisoned or involuntarily incarcerated for the treatment of either a psychiatric or physical illness).

If study intervention is discontinued prior to the participant's completion of the study, the reason for the discontinuation must be documented in the participant's medical records per local regulatory requirements in each region/country and entered on the appropriate eCRF page.

### **8.1.1      *Dose Discontinuation***

Study treatment must be permanently discontinued per criteria in [Table 7.4.1-1](#) in [Section 7.4](#).

Discontinue study treatment for any AE, laboratory abnormality, or intercurrent illness which in the judgment of the Investigator, presents a substantial clinical risk to the participant with continued dosing.

Any event that leads to delay in dosing lasting > 10 weeks from the previous dose requires discontinuation of study drug, with the following exceptions:

- Dosing delays to allow for prolonged steroid tapers to manage drug-related AE are allowed.
- Dosing delays lasting > 10 weeks from the previous dose that occur for non-drug-related reasons may be allowed if approved by the Medical Monitor/ designee.

Note: dosing delays that are approved by the Medical Monitor/designee must be documented.

### **8.1.2 Post-study Intervention Study Follow-up**

In this study, RFS is a key endpoint of the study. Post-study follow-up is of critical importance and is essential to preserving participant safety and the integrity of the study. Participants who discontinue study intervention must continue to be followed (in this study or a rollover study) for collection of outcome and/or survival follow-up data as required and in line with [Section 5.3](#) until death or the conclusion of the study.

BMS may request that survival data be collected on all randomized participants outside of the protocol defined window as defined in [Section 2](#). At the time of this request, each participant will be contacted to determine their survival status unless the participant has withdrawn consent for all contacts or is lost to follow-up.

## **8.2 Discontinuation From the Study**

Participants who request to discontinue study intervention will remain in the study and must continue to be followed for protocol-specified follow-up procedures. The only exception to this is when a participant specifically withdraws consent for any further contact with him/her or persons previously authorized by participant to provide this information.

- Participants should notify the investigator of the decision to withdraw consent from future follow-up.
- The withdrawal of consent should be explained in detail in the medical records by the investigator, as to whether the withdrawal is from further treatment with study intervention only or also from study procedures and/or post-treatment study follow-up, and entered on the appropriate eCRF page.
- In the event that vital status (whether the participant is alive or dead) is being measured, publicly available information should be used to determine vital status only as appropriately directed in accordance with local law.
- If the participant withdraws consent for disclosure of future information, the Sponsor may retain and continue to use any data collected before such a withdrawal of consent.

### **8.2.1 Individual Discontinuation Criteria**

- A participant may withdraw completely from the study at any time at his/her own request, or may be withdrawn at any time at the discretion of the investigator for safety, behavioral, compliance, or administrative reasons. This is expected to be uncommon. Stopping study intervention is not considered withdrawal from the study.
- Site should document if subject is unwilling to attend future visits, accept phone calls, allow contact with their personal physician, or allow review of medical records for health status information.

- At the time of discontinuing from the study, an immediate follow-up visit may be needed. See the Schedule of Activities ([Section 2](#)) for data to be collected at the time of study discontinuation and follow-up and for any further evaluations that need to be completed.
- The participant will be permanently discontinued both from the study intervention and from the study at that time.
- If the participant withdraws consent for disclosure of future information, the Sponsor may retain and continue to use any data collected before such a withdrawal of consent.

### **8.3 Lost to Follow-up**

The following actions must be taken if a participant fails to return to the clinic for a required study visit:

- All reasonable efforts must be made to locate participants to determine and report their ongoing status. This includes follow-up with persons authorized by the participant.
- Lost to follow-up is defined by the inability to reach the participant after a minimum of **three (3)** documented phone calls, faxes, or emails, as well as lack of response by participant to one (1) registered mail letter. All attempts should be documented in the participant's medical records.
- If it is determined that the participant has died, the site will use permissible local methods to obtain date and cause of death.
- If the investigator's use of third-party representative to assist in the follow-up portion of the study has been included in the participant's informed consent, then the investigator may use a Sponsor-retained third-party representative to assist site staff with obtaining the participant's contact information or other public vital status data necessary to complete the follow-up portion of the study.
- The site staff and representative will consult publicly available sources, such as public health registries and databases, in order to obtain updated contact information.
- If, after all attempts, the participant remains lost to follow-up, then the last known alive date as determined by the investigator should be reported and documented in the participant's medical records.

## **9 STUDY ASSESSMENTS AND PROCEDURES**

Study procedures and timing are summarized in the Schedule of Activities.

Protocol waivers or exemptions are not allowed.

All immediate safety concerns must be discussed with the Sponsor immediately upon occurrence or awareness to determine if the participant should continue or discontinue treatment.

Adherence to the study design requirements, including those specified in the Schedule of Activities, is essential and required for study conduct.

All screening evaluations must be completed and reviewed to confirm that potential participants meet all eligibility criteria before randomization. The investigator will maintain a screening log to

record details of all participants screened and to confirm eligibility or record reasons for screening failure, as applicable.

Procedures conducted as part of the participant's routine clinical management (e.g., blood count) and obtained before signing of informed consent may be utilized for screening or baseline purposes provided the procedure meets the protocol-defined criteria and has been performed within the timeframe defined in the Schedule of Activities.

Perform additional measures, including non-study required laboratory tests, should be performed as clinically indicated or to comply with local regulations. Laboratory toxicities (eg, suspected drug induced liver enzyme evaluations) will be monitored during the follow-up phase via on site/local labs until all study drug related toxicities resolve, return to baseline, or are deemed irreversible.

Evaluate participant immediately to rule out cardiac or pulmonary toxicity if participant shows cardiac or pulmonary-related signs (hypoxia, abnormal heart rate or changes from baseline) or symptoms (eg, dyspnea, cough, chest pain, fatigue, palpitations).

Some of the assessments referred to in this section may not be captured as data in the eCRF. They are intended to be used as safety monitoring by the treating physician. Additional testing or assessments may be performed as clinically necessary or where required by institutional or local regulations.

The maximum amount of blood collected from each participant over the duration of the study, including any extra assessments that may be required, will be at approximately 775 mL. However, the volume of blood drawn for local safety assessments, done before every dose, and in follow-up, will depend on local institutional practices and will vary from institution to institution.

## **9.1 Efficacy Assessments**

### **9.1.1 Efficacy Assessment for the Study**

Study evaluations will take place in accordance with [Section 2](#), Schedule of Activities. Surveillance for recurrence will be performed until investigator assessed [REDACTED]  
recurrence [REDACTED]

Contrast-enhanced CT of the chest, abdomen, pelvis, and all suspected sites of disease must be performed every 12 weeks ( $\pm$  7 days) from randomization for the first 2 years, and every 26 weeks ( $\pm$  14 days) beyond the Week 108 imaging time point thereafter until investigator assessed [REDACTED]

Imaging should be obtained anytime there is suspected disease. In cases of suspected lesions of the extremities, contrast-enhanced MRI may be substituted for contrast-enhanced CT. Please refer to [Appendix 9](#) for Germany-specific imaging language.

Participants with a history of brain metastasis or symptoms should have a surveillance MRI (without and with contrast) approximately every 12 weeks  $\pm$  7 days from randomization for the first 2 years and subsequently every 26 weeks ( $\pm$  14 days) beyond the Week 108 imaging time point thereafter until investigator assessed [REDACTED] recurrence [REDACTED]  
[REDACTED] or sooner if clinically indicated. Participants without history of brain metastases should have MRI if clinically indicated.

### **9.1.2 Imaging Assessment for the Study**

Images will be submitted to a central imaging vendor and may undergo blinded independent central review (BICR) at any time during the study. Prior to scanning the first participant, sites should be qualified and understand the image acquisition guidelines and submission process as outlined in the Imaging Manual provided by the central imaging vendor.

Screening and on-study images should be acquired as outlined in [Section 2](#), Schedule of Activities. Tumor assessments at other time points may be performed if clinically indicated and should be submitted to the central imaging vendor as soon as possible. All imaging that may demonstrate disease recurrence (including scans performed at unscheduled time points and/or at an outside institution) should be collected and submitted to the imaging vendor.

Assessments for recurrence should continue on the protocol defined imaging schedule regardless if dosing is delayed or discontinued. [REDACTED]  
[REDACTED]  
[REDACTED]

The same method of assessment used at Screening should be used for on-study time points. CT images should be acquired with slice thickness of 5 mm or less with no intervening gap (contiguous). Every attempt should be made to image each participant using an identical acquisition protocol on the same scanner for all imaging time points.

- If a participant has a contraindication for CT intravenous contrast, then a non-contrast CT of the chest and a contrast-enhanced MRI of the abdomen, pelvis, and suspected sites of disease should be obtained.
- If a participant has a contraindication for both MRI and CT intravenous contrasts, then a non-contrast CT of the chest and a non-contrast MRI of the abdomen, pelvis, and other suspected sites of disease should be obtained.
- If a participant has a contraindication for MRI (eg, incompatible pacemaker) in addition to contraindication to CT intravenous contrast, then a non-contrast CT of the chest, abdomen, pelvis, and suspected sites of disease is acceptable.

MRI of brain (without and with contrast) must be acquired as outlined in [Section 2](#) (Schedule of Activities). CT of the brain (without and with contrast) can be performed if MRI is contraindicated.

[figure not shown]
Other imaging may be collected per local standards, as clinically indicated. See [Section 7.7.2.2](#).

**Use of CT component of a PET-CT scanner:** Combined modality scanning such as with positron emission tomography-computed tomography (PET-CT) is increasingly used in clinical care, and is a modality/technology that is in rapid evolution; therefore, the recommendations outlined here may change rather quickly with time. At present, low dose or attenuation correction CT portions of a combined PET-CT are of limited use in anatomically-based efficacy assessments and it is therefore suggested that they should not be substituted for dedicated diagnostic contrast enhanced CT scans for anatomically-based measurements. However, if a site can document that the CT performed as part of a PET-CT is of identical diagnostic quality to a diagnostic CT (with intravenous and oral contrast), then the CT portion of the PET-CT can be used for measurements. Note, however, that the PET portion of the CT introduces additional data which may bias an investigator if it is not routinely or serially performed.

### **9.1.3      *Investigator Assessment of Baseline Disease Status***

Participant eligibility (disease-free status) must be confirmed by investigator prior to randomization. Baseline disease assessments should be performed within 35 days prior to randomization, including contrast-enhanced CT of the chest, abdomen, pelvis, and all suspected sites of disease. Baseline MRI of the brain (with and without contrast) is required for ALL participants during screening to rule out brain metastases, within 35 days prior to randomization. CT of the brain (without and with contrast) can be performed if MRI is contraindicated. Please refer to [Appendix 9](#) for Germany-specific imaging language.

All participants must have disease-free status defined as no clinical or radiographic evidence of recurrence of disease documented by a complete physical examination within 14 days prior to randomization and imaging studies within 35 days prior to randomization.

[figure not shown]
### **9.1.4      *Investigator Assessment of Recurrence***

[figure not shown]
The same method of assessment used at Screening should be used for on-study time points. Post-baseline assessments will be performed at the time points described in [Table 2-2](#) and [Table 2-3](#) until  recurrence 

Tumor assessments for ongoing study treatment decisions will be completed by the investigator. Additional imaging of potential disease sites should be performed whenever disease recurrence or occurrence of a secondary malignancy is suspected.

Cytology and/or histology are mandatory to confirm recurrence in solitary or in doubtful/suspect lesions, cutaneous, subcutaneous, or lymph node lesions. Histological or cytological evidence of recurrence should be attempted in all cases, except for brain metastases, when safe and clinically feasible. Tumor markers or auto-antibodies alone cannot be used to assess recurrence.

[REDACTED]

### **9.1.5      *Patient-Reported Outcomes***

Health-related quality of life (HRQoL) will be assessed by [REDACTED]

[REDACTED] in participants who are  $\geq$  18 years of age at the time of informed consent as outlined in [Section 2](#). Adolescent participants ( $\geq$  12 and  $<$  18 years of age) only complete [REDACTED]. Adolescent participants will continue to complete only the [REDACTED] even if they become  $\geq$  18 years of age during treatment or follow-up.

If Health Outcomes Assessments are collected but the dose is subsequently delayed, a data change form should be submitted to move the original data entry to an unscheduled visit.

If the participant withdraws from the study prematurely, all attempts should be made to obtain [REDACTED] prior to withdrawal from the study in participants who are  $\geq$  18 years of age at the time of informed consent, or [REDACTED] for participants who are  $\geq$  12 and  $<$  18 years of age at the time of informed consent. Reasons for missing patient-reported outcomes questionnaires should also be documented so that the appropriate imputation method can be employed to correct for missing data in the analysis.

[figure not shown]
The questionnaire will be completed by the participants before any clinical assessments are performed and treatments administered at any given visit. If participants refuse to complete all or any part of a questionnaire, this will be documented. Questionnaires should be completed in the language most familiar to each participant (if available), and participants should be given adequate time and space to complete the questionnaire. In order to preserve the integrity of trial data, no patient-reported data can be changed after the patient initially provides it.

[REDACTED] assessments in Long-term Follow Up (visits beyond Follow Up 2) may be completed by other modes of administration (eg, telephone) if deemed necessary by the study team. If exceptional circumstances preclude the continued administration of measures using planned modalities, then alternate administration methods may be required, after consultation with the Sponsor.

[REDACTED]

[REDACTED]

[REDACTED]

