**Table 2-2: On Study Treatment Procedural Outline (CA224098)**

Procedure	C1D1 a (Cycle Duration = 4 weeks)	C2D1 and D1 of Each Subsequent Cycle ( $\pm$ 3 days)	Notes: b
[REDACTED]	[REDACTED]	[REDACTED]	[REDACTED]

Abbreviations: AE, adverse event; C, cycle; CLND, complete lymph node dissection;

D, day; eCOA, electronic clinical outcome assessments; ECOG, Eastern Cooperative Oncology Group;

HCG, human chorionic gonadotropin; IMAE, immune-mediated adverse event; IRT, interactive response technology;

MRI, magnetic resonance imaging; [REDACTED] SAE, serious adverse event; [REDACTED]

[REDACTED] WOCBP, women of child-bearing potential.

a If a dose is delayed, the procedures scheduled for that same time point should also be delayed to coincide with when that time point's dosing actually occurs, with the exception of tumor assessments which should occur as scheduled.

b Some of the assessments referred to in this section may not be captured as data in the eCRF. They are intended to be used as safety monitoring by the treating physician. Additional testing or assessments may be performed as clinically necessary or where required by institutional or local regulations.

c Screening assessments performed within 3 days of first dose are not required to be repeated at C1D1.

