### **7.1.1      *Study Treatment Details***

Participants will receive nivo + rela FDC or nivolumab monotherapy on Day 1 of every 4-week cycle. Blinded study drug will be administered in a single bag IV over approximately 30 minutes. Participants should be carefully monitored for infusion reactions during IV administration. If an acute infusion reaction is noted, participant should be managed according to [Section 7.4.4](#).

- There will be no dose escalations or reductions of immunotherapy allowed.
- Premedications are not recommended for the first dose of immunotherapy.
- Participants should be carefully monitored for infusion reactions during immunotherapy administration.
- If an acute infusion reaction is noted, participants should be managed according to [Section 7.4.4](#).
- Participants should receive immunotherapy until recurrence [REDACTED], unacceptable toxicity, withdrawal of consent, a maximum treatment duration of 1 year from first dose (maximum of 13 doses), or the study ends, whichever occurs first.
- Doses of immunotherapy may be interrupted, delayed, or discontinued depending on how well the participant tolerates the treatment according to [Section 7.4.1](#).
- Dosing visits must not be skipped, only delayed. See [Section 7.4](#) and [Section 8.1](#).

All infusions must be promptly followed by a diluent flush to clear the line of IP before starting infusion(s) of any additional treatment. Instruction for dilution and infusion of study drug injections will be provided in the Pharmacy Manual. Care must be taken to assure sterility of the prepared solution as the product does not contain any antimicrobial preservative or bacteriostatic agent. For details on prepared drug storage, preparation, and administration, please refer to the IBs and/or Pharmacy Manual. The selection and timing of dose for each participant is provided in [Table 7.1-1](#).

Study treatment will be dispensed by interactive response technology (IRT) at the study visits as listed in [Section 2](#) (Schedule of Activities). Further details regarding preparation and administration will be provided separately in site/pharmacy training materials.

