**Table 7.4.1-1: Adverse Event Criteria for Delay, Resume, and Discontinue of Treatment**

Drug-Related Adverse Event (AE) per CTCAE V5	Severity	Action Taken	Clarifications, Exceptions, and Resume Criteria
Gastrointestinal			
Colitis or Diarrhea	Grade 2	Delay dose	Dosing may resume when AE resolves to baseline
	Grade 3	Delay dose	Dosing may resume when AE resolves to baseline
	Grade 4	Permanently discontinue	
Renal			
Serum Creatinine Increased	Grade 2 or 3	Delay dose	Dosing may resume when AE resolves to Grade $\leq$ 1 or baseline value
	Grade 4	Permanently discontinue	
Pulmonary			
Pneumonitis	Grade 2	Delay dose	Dosing may resume after pneumonitis has resolved to $\leq$ Grade 1.
	Grade 3 or 4	Permanently discontinue	
Hepatic			
Aspartate aminotransferase (AST), alanine aminotransferase (ALT), or total bilirubin (T.bili) increased	AST or ALT $> 3 \times$ and $\leq 5 \times$ upper limit of normal (ULN) or T.bili $> 1.5 \times$ and $\leq 3 \times$ ULN, regardless of baseline value	Delay dose	Dosing may resume when laboratory values return to baseline.
	AST or ALT $> 5 \times$ ULN or T.bili $> 3 \times$ ULN, regardless of baseline value	Permanently discontinue	
	Concurrent AST or ALT $> 3 \times$ ULN and T.bili $> 2 \times$ ULN, regardless of baseline value	Permanently discontinue	

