**Table 7.4.1-1: Adverse Event Criteria for Delay, Resume, and Discontinue of Treatment**

Drug-Related Adverse Event (AE) per CTCAE V5	Severity	Action Taken	Clarifications, Exceptions, and Resume Criteria
Endocrinopathy			
Adrenal Insufficiency	Grade 2 adrenal insufficiency	Delay dose	Dosing may resume after adequately controlled with hormone replacement.
	Grade 3 or 4 adrenal insufficiency or adrenal crisis	Delay dose or permanently discontinue	Mandatory discussion with and documented approval from the Medical Monitor/designee needed prior to resuming therapy. If adrenal insufficiency resolves or is adequately controlled with physiologic hormone replacement, participant may not require discontinuation of study drug.
Hyperglycemia	Hyperglycemia requiring initiation or change in daily management (Grade 2 or 3)	Delay dose	Dosing may resume if hyperglycemia resolves to Grade $\leq$ 1 or baseline value, or is adequately controlled with glucose-controlling agents.
	Grade 4	Delay dose or permanently discontinue	Mandatory discussion with and documented approval from the Medical Monitor/designee needed prior to resuming therapy. If hyperglycemia resolves, or is adequately controlled with glucose-controlling agents, participant may not require discontinuation of study drug.
Hypophysitis/Hypopituitarism	Symptomatic Grade 1-3 that is also associated with corresponding abnormal lab and/or pituitary scan	Delay dose	Dosing may resume if endocrinopathy resolves to be asymptomatic, or is adequately controlled with only physiologic hormone replacement.
	Grade 4	Delay dose or permanently discontinue	Mandatory discussion with and documented approval from the Medical Monitor/designee needed prior to resuming therapy. If endocrinopathy resolves or is adequately controlled with physiologic hormone replacement, participant may not require discontinuation of study drug.
Hyperthyroidism or Hypothyroidism	Grade 2 or 3	Delay dose	Dosing may resume if endocrinopathy resolves to be asymptomatic, or is adequately controlled with only physiologic hormone replacement or other medical management.
	Grade 4	Delay dose or permanently discontinue	Mandatory discussion with and documented approval from the Medical Monitor/designee needed prior to resuming therapy. If endocrinopathy resolves or is adequately controlled with physiologic hormone replacement or other medical management, participant may not require discontinuation of study drug.

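### Does moving a questionnaire to an unscheduled visit after a dose delay distort the HRQoL comparison?

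*Combined protocol and SAP*

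**What the plan says.** Section 9.1.5 places the questionnaire first at any visit, ahead of clinical assessments and treatment. When the form has been collected and the dose is then delayed, "a data change form should be submitted to move the original data entry to an unscheduled visit". The same section bars any alteration of patient-reported answers once given, and asks for the reasons for missing questionnaires so that imputation can be chosen.

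Footnote a of Table 2-2 says that when a dose is delayed "the procedures scheduled for that same time point should also be delayed" to the day dosing takes place, "with the exception of tumor assessments which should occur as scheduled". Section 7.1.1 adds: "Dosing visits must not be skipped, only delayed".

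Table 7.4.1-1 ties restarting to the state of the event. For Grade 2 or 3 colitis or diarrhea, "Dosing may resume when AE resolves to baseline"; for Grade 2 adrenal insufficiency, "Dosing may resume after adequately controlled with hormone replacement". Section 8.1.1 limits the interval: "Any event that leads to delay in dosing lasting > 10 weeks from the previous dose requires discontinuation of study drug". There are exceptions, among them "Dosing delays to allow for prolonged steroid tapers to manage drug-related AE are allowed".

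Table 4-1 shows no HRQoL endpoint among its visible primary and secondary entries, and its exploratory rows are redacted. Section 10.4 leaves technical detail to an SAP that is to be final before the primary endpoint database lock.

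**The concern.** Read together, these rules tie the visit label to health after randomization. A participant who feels ill completes the form on the planned day, the dose is withheld, and that form loses its cycle label. Weeks later, once the event has resolved or been controlled, a second form is completed on the dosing day and takes the label. If dosing never resumes, the cycle has no labelled form at all.

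An analysis by nominal visit that ignored unscheduled records would then tend to drop low scores and keep recovered ones. If the combination arm had more health-related delays, part of a real quality-of-life deficit in that arm could be hidden. Scores under one label would also come from different times since randomization. The protocol keeps imaging on its calendar despite dose delays, so the lack of a visible exemption for questionnaires looks like an oversight.

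**Working it through.** The visible text gives no HRQoL effect size, SD, completion rate or delay rate, so there is no planned figure to reproduce. The check has four parts.

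**1. Which rule creates the effect.** Footnote a, if it governs questionnaires, generates a form on the dosing day. The relocation sentence decides what happens to the earlier form: it is kept, under another label. Without relocation, two forms would compete for one cycle. The sentence criticised therefore preserves the pre-delay score and avoids a duplicate.

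Whether footnote a alone governs questionnaire timing cannot be seen. Appendix 10 shows that Amendment 02 introduced the relocation sentence together with another Health Outcomes instruction, which is redacted.

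**2. Timing.** Inputs: a 4-week cycle (Table 2-2) and 10 weeks from the previous dose (Section 8.1.1).

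- Largest ordinary shift: 10 − 4 = 6 weeks = 42 days, longer under the exceptions.
- Assume a form every 28 days and windows of ±14 days (28/2). A delay under 14 days leaves both forms in the same window, where a tie rule chooses. A delay between 14 and 42 days (28 + 14 = 42) puts the second form in the next window and leaves the moved form alone in its own.

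Ordinary date-based windowing thus recovers the pre-delay score, provided the completion date stays with the moved entry.

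**3. Size if nominal labels were used and unscheduled records dropped.** The shift in the between-arm mean difference at one visit is (pT − pC) × D. Here pT and pC are the shares with a relocated form in the combination and nivolumab arms, and D is the score loss on the planned day that has recovered by the dosing day.

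As a proxy, take Grade 3-4 drug-related event rates of 18.9% and 9.7% (Section 3.2.6, advanced melanoma). Assume one delay per affected participant, spread evenly over Cycles 2 to 13 (12 visits), and D of 10 to 20 points on a 0-100 scale.

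- Difference per visit: (18.9 − 9.7)/12 = 0.77 percentage points.
- D = 10: 0.00767 × 10 = 0.08 points.
- D = 20: 0.00767 × 20 = 0.15 points.
- Half recovery: 0.04 to 0.08 points.
- If the share of delays with any score drop runs from 0% to 100%, the range is 0 to 0.15 points.

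Heavier assumptions give more:

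| pT / pC at one visit | D | Shift (points) |
|---|---|---|
| 5% / 3% | 10 | 0.02 × 10 = 0.20 |
| 10% / 5% | 10 | 0.05 × 10 = 0.50 |
| 18.9% / 9.7% | 10 | 0.092 × 10 = 0.92 |
| 18.9% / 9.7% | 20 | 0.092 × 20 = 1.84 |

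The last two rows load a cumulative rate onto a single visit. They are extreme cases for that proxy and could not hold at every visit.

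**4. Against sampling error.** Assume SD 20. The standard error of a difference in means is 20 × √(2/n).

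- n = 500 per arm: 1.26 points.
- n = 300 per arm: 1.63 points.

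The evenly spread illustration peaks at 0.15/1.26 = 0.12 of a standard error. The 0.92-point row stays below one standard error; only the 1.84-point row exceeds it.

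**The case for a change.** The best argument for changing the plan is that the mechanism is real and the remedy cheap. One sentence in the SAP could assign all forms to windows by completion date, with a tie rule fixed before unblinding, and relocated forms could be counted by arm. It would also stop a completed form from being treated as missing and imputed when dosing never resumes. The proxy could understate the problem, because many Grade 2 events in Table 7.4.1-1 trigger a delay and are not counted in it.

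Much of this stands as description. Date-based mapping with a tie rule is sound practice, and it is sensible to check that unscheduled forms enter the mapping. What is missing is evidence that the plan does otherwise. The text that would settle it is redacted or not supplied, and absence for that reason is not a gap in the plan.

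The proxy also errs in the other direction. Many Grade 3-4 events lead to permanent discontinuation rather than delay, and many delay triggers are laboratory values that need not lower quality of life. Because laboratory tests may be drawn up to 3 days before dosing, some delays are decided before any form exists.

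It might also be argued that forms from before Amendment 02 carry labels set under a different rule. Nothing visible shows this. Appendix 10 gives the reason for that group of changes as alignment with the sponsor's current processes and clarity, which fits writing down existing practice at least as well.

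**Conclusion.** The concern does not call for a change. The cycle label can depend on fitness to be dosed if footnote a applies to questionnaires, but a label is not an analysis. Harm needs an HRQoL analysis that uses nominal visits and also discards unscheduled records, and no visible text specifies one. The relocated score survives, and choosing a visit window and a tie rule is routine work that the SAP may already cover.

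Under the evenly spread illustration the effect is 0 to 0.15 points per visit, about a tenth of a standard error at most. That rests on an assumed 0-100 scale, SD 20, 300 to 500 forms per arm, a form at every cycle, and event rates borrowed from advanced disease in place of unknown delay rates. Only loading the whole cumulative rate onto one visit, with a 20-point drop fully recovered, takes the shift above one standard error.

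The likely direction, if any, is to flatter the arm with more health-related delays, though this is not certain. RFS, OS, DMFS and adverse event analyses are unaffected.
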